10.1.5 Response Criteria

10.1.5.1 Evaluation of Target Lesions

Volumetric Analysis

As previously described [48], volumetric response will be determined by measuring measurable and non measurable primary and nodal disease in at least two dimensions as determined by scan, clinical exam or pathology. If measurement in two dimensions is not possible due to irregular shape of the lesion, comparison of the single largest dimension measured may be used. In all cases, serial photographs are strongly recommended to help assess response. Responders will have demonstrated any decrease in overall tumor volume. Primary and nodal volume will also be assessed separately in terms of response.

RECIST Criteria

Complete Response (CR): Disappearance of all target lesions.

Partial Response (PR): At least a 30% decrease in the sum of the longest diameter (LD) of target lesions, taking as reference the baseline sum LD.

Progressive Disease (PD): At least a 20% increase in the sum of the longest diameter (LD) of target lesions, taking as reference the smallest sum LD recorded since the treatment started or the appearance of one or more new lesions (new lesions must be > slice thickness).

Stable Disease (SD): Neither sufficient shrinkage to qualify for PR nor sufficient increase to qualify for PD, taking as reference the smallest sum LD since the treatment started.

Unknown (UN): Assessment of target lesions cannot be made due to insufficient or unevaluable data. In this case, a concise explanation must be given.

Note: If tumor response data is missing for target lesions, the overall assessment must be UN unless there is new disease that would result in an overall assessment of PD. However, if there is missing or unevaluable data for non-target lesions, but data is available for all target lesions, the overall response for that time point will be assigned based on the sum LD of all target lesions. Additionally, the assessment of CR cannot be made if there is missing or unevaluable data for non-target lesions. In this case, the overall assessment would be PR.

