14. STATISTICAL CONSIDERATIONS

This sequential biomarker driven screening design is designed to identify promising treatments worthy of additional study.

Co Primary Endpoint

The primary endpoints for this trial is safety and tolerability defined as the number of DLTs and volumetric response as defined in section 10.1.

Secondary Endpoints:

Secondary endpoints include disease response according to RECIST 1.1, pathologic response, local failure rate, regional failure rate, local and regional progression free survival, disease-free survival, and overall survival. All are defined in Section 10.1.

Sample Size and Study Duration:

Because the use of nivolumab with or without ipilimumab is relatively novel in this setting, we will complete a safety run-in prior in each cohort prior to enrolling additional patients. If a single patient in either cohort is permanently unable to undergo surgery as a result of investigational treatment, enrollment to that cohort will close other DLTs are defined in Section 5.4. If this occurs in the nivolumab cohort then the study will close. The safety run in will begin and complete for nivolumab cohort before enrollment begins on the safety-run in ipilimumab cohort. Once both safety run-ins are complete, patients will be randomized to one of the two cohorts. If at any point during the study only one cohort is open for enrollment, all patients will be assigned to that cohort.

The safety run in for each cohort will follow a typical 3+3 design in each cohort. Initially 3 patients will be entered. If 0 out of 3 patients experiences dose-limiting toxicity (DLT), the safety run in will end and the study will proceed. If exactly 1 out of 3 patients has a DLT, an additional 3 patients will be entered in the safety run in. If none of the next 3 patients experiences a DLT, the study will proceed. If at any time 2 (or more) patients experience DLT, the study will terminate. Either arm will be considered promising if the safety run in is successfully completed.

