Additionally, either arm (nivolumab or nivolumab combined with ipilimumab) will be considered promising and worthy of further evaluation if there is strong evidence that the response rate in either arm evaluated independently may be at least 15% (number of patients with volumetric response versus total number of patients treated in that arm). Response rates will also be correlated with RECIST and pathologic response and changes in lymphocyte infiltration of primary tumor deposits.

The decision rule will be based on the lower bound of the one-sided, 90% exact binomial confidence interval. With this criteria, the treatment will be considered promising if 6 or more of the 20 patients (including patients in the safety-run in) in either arm demonstrate a response. This

would correspond to a lower confidence bound that is at least 15%. If none of the first 10 patients in either arm have a response, then enrollment will stop. Analyses of response rates will be presented by treatment arm within disease accompanied by exact 80% confidence intervals. For a sample of size 20 per arm, each confidence interval will be no wider than 0.32. We will also estimate an aggregated response rate for each treatment modality and present with 80% exact confidence intervals.

Correlative studies will be largely exploratory in nature. We will attempt to correlate PD-L1 expression, mutational burden, T-cell infiltration and initial tumor burden with volumetric, RECIST and pathologic response. We will measure changes in radiologic and pathologic parameters and IHC staining over the course of therapy and correlate these with response and changes in immune markers present in the peripheral circulation.

The accrual goal for this study is 40 patients. We anticipate enrolling approximately 2 patients per month. Therefore, we expect to completely accrue to this study in approximately 20 months. The results should be made public within 24 months of reaching the end of the study. The end of the study is the time point at which the last data items are reported or after the outcome data are sufficiently mature for analysis, as defined above.

Analysis of Endpoints:

The primary endpoint is volumetric response, which will be assessed among all patients who initiate protocol therapy. Response will be assessed as defined in section 10.1. The response rate will be reported with 90% exact confidence intervals.

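### The 6/20 rule counts any shrinkage as response against an unjustified 15%, lets pathologic size into the primary comparison, and coexists with a route to promising that needs no response

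*Combined protocol and SAP*

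**What the plan says.** Section 10.1.5.1 bases volumetric response on "measuring measurable and non measurable primary and nodal disease in at least two dimensions as determined by scan, clinical exam or pathology". For irregular lesions, "comparison of the single largest dimension measured may be used". The threshold is zero: "Responders will have demonstrated any decrease in overall tumor volume". Section 1.2 describes the same endpoint as a product of the two longest diameters.

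Section 14 looks for "strong evidence that the response rate in either arm evaluated independently may be at least 15"%, with the rate defined as "number of patients with volumetric response versus total number of patients treated in that arm". Using a one-sided 90% exact bound, "the treatment will be considered promising if 6 or more of the 20 patients" respond. An arm with no responder among its first 10 patients stops enrolling. Section 14 also states: "Either arm will be considered promising if the safety run in is successfully completed".

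On method, Sections 10.1 and 10.1.5.1 both list pathology as a source for the primary measurement. Section 10.1.2 gives a reason: oral-cavity imaging may be obscured by dental artifact or normal mucosa, so exam or pathologic measurements may be enough. Section 10.1.3 asks for the same method and technique at baseline and follow-up, and ranks imaging above clinical exam. It gives pathology no rank. Section 10.1 places the response re-evaluation before definitive surgery, and Section 10 places pathologic evaluation at surgery.

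**The concern.** Section 14 describes the trial as "designed to identify promising treatments worthy of additional study". Readers will take a promising result as evidence of drug activity. With a zero threshold, measurement error alone can produce responders, so the 15% benchmark limits error against an inactive arm only if few unaffected tumours would appear smaller. The plan gives no such rate and no allowance for measurement error. Reference 48 is cited for the measurement approach; it is not attached to the 15%.

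Mixing methods makes this worse. If a baseline scan or exam is compared with a specimen measurement, any systematic difference between the methods is counted as shrinkage or growth, and under this definition any difference decides the patient's status.

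The run-in sentence raises a different problem: it gives the same label to an arm that need not have had any response.

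**Working it through.** **1. The plan's own figure.** Inputs from Section 14: n = 20, cut-off 6, one-sided 90% exact bound. The bound is the p that solves P(X ≥ x | 20, p) = 0.10. For x = 5 it is 12.7%; for x = 6 it is 16.6%. Six is therefore the smallest count with a bound of at least 15%, as the plan says.

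**2. Chance of passing.** P(promising) = Σ over a = 1 to 10 of P(A = a) × P(B ≥ 6 − a), where A and B are independent Binomial(10, p) counts for the first and second ten patients. P(stop) = (1 − p)^10.

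| True any-decrease rate | P(stop at 0/10) | P(promising) |
|---|---|---|
| 15% | 19.7% | 6.7% |
| 16.6% | 16.3% | 10.0% |
| 20% | 10.7% | 19.5% |
| 25% | 5.6% | 38.2% |
| 30% | 2.8% | 58.2% |
| 50% | 0.1% | 97.9% |

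These are error rates only if the rate in the first column arises without drug effect. Error stays at or below 10% only while that no-effect rate is at most about 16.6%.

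**3. What the no-effect rate might be (assumed inputs).** The documents give neither tumour growth nor measurement error. Assume log-normal error with coefficient of variation CV on each measured product, independent at the two visits, and true growth g in the product. Then s = √(2 ln(1 + CV²)) and P(decrease) = Φ(−ln(1 + g)/s).

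- g = 0, any CV: 50%, so P(promising) = 97.9%.
- g = 10%, CV 15%: s = 0.211, ln 1.10 = 0.0953, rate 32.6%, P(promising) = 68%.
- g = 20%, CV 10%: s = 0.141, ln 1.20 = 0.1823, rate 9.8%, P(promising) = 1%.
- g = 20%, CV 5%: rate 0.5%, P(promising) below 0.1%.

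Plausible-looking inputs cover nearly the whole range, so the documents cannot settle the error.

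**4. Pathologic size.** Side by side: the whole-tumour specimen is measured only after window treatment, so its baseline has to be a scan or exam (Sections 10 and 10.1.5.1); the method should be the same at both times (10.1.3); re-evaluation precedes surgery (10.1). All three cannot hold for a patient whose follow-up size is pathologic. To illustrate, assume every follow-up size is pathologic, with CV 10% and growth 20%:

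- No between-method difference: rate 9.8%, P(promising) 1%.
- Pathology reads the product 10% lower: ln(1.20 × 0.90) = 0.0770, rate 29.3%, P(promising) 55%.
- Pathology reads it 10% higher: ln(1.20 × 1.10) = 0.2776, rate 2.5%, P(promising) below 0.1%.

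An offset can therefore create responders or hide them.

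**5. Run-in route.** With DLT probability d (assumed) and q = 1 − d, the 3+3 completes with probability q³ + 3dq² × q³ = q³ + 3dq⁵, before the separate rule on inability to undergo surgery:

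- d = 10%: 0.729 + 0.177 = 91%.
- d = 20%: 0.512 + 0.197 = 71%.
- d = 30%: 0.343 + 0.151 = 49%.

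Response does not enter this calculation.

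**The case against.** The strongest reply is that 15% is the null: this is a small screening trial and the rule does what it says. As a test of the any-decrease rate that is right, and nothing in the binomial calculation needs correcting. It does not make 15% a no-effect rate, which is what a claim of activity needs.

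A second reply is that safeguards exist. Imaging is preferred to exam, serial photographs are recommended, and RECIST and pathologic response are planned secondary endpoints. Growth before restaging also works against chance decreases. All of this stands, but none of it enters the 6/20 call, and Section 10.1.10 rules out central review.

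Third, pathology is a reasoned fallback to a rule worded as *should*. The reason is genuine, and how often the fallback would be used is unknown. But clinical exam is offered in the same sentence for the same difficulty and can be done at both time points. The plan neither exempts pathology from the same-method rule nor says when it takes precedence.

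Fourth, safety is co-primary, and Section 14 introduces the response criterion as an additional one, so two senses of promising may be intended. That is possible, but the text does not separate them.

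A reader might infer that an inactive arm would usually pass. The documents do not support this: the 97.9% needs no true growth and symmetric error, and step 3 gives results below 0.1% under other assumptions.

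**Conclusion.** The point holds as a gap in justification and two internal inconsistencies. It is not a calculation error. Three statements are secure from the text:

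- 6/20 shows, at the plan's own confidence level, that the any-decrease rate exceeds 15%, and no more than that.
- Pathologic size is admitted to the primary comparison in conflict with Sections 10.1 and 10.1.3.
- Read literally, an arm with no responders can be called promising.

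The size of the error against an inactive arm is unknown. It is 6.7% if the no-effect rate is 15% and rises to 38%, 58% and 97.9% at 25%, 30% and 50%. Those rates, and the growth, CV, between-method offset and DLT values used above, are all assumptions. The 0/10 stop depends on the same unknown: it triggers with probability 19.7% at a 15% rate and 0.1% at 50%.

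A reader might also infer that a minimum-decrease threshold is required. The documents supply no measurement error from which to set one, so it remains a choice for the sponsor.

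**What to change.** (a) In Sections 10.1, 10.1.2 and 10.1.5.1, require the same modality at baseline and before surgery for the primary volumetric endpoint: imaging, or clinical exam at both times where imaging is obscured. Keep pathologic size for the pathologic endpoint or a labelled sensitivity analysis.

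(b) In Section 14, either justify 15% as the expected rate of any decrease without drug effect, or state that 6/20 shows only that the any-decrease rate exceeds 15% and does not control error against an inactive arm. If the justification leads to a higher rate, the same bound criterion needs 7/20 at 20%, 10/20 at 30% and 14/20 at 50%.

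(c) In Section 14, say that completing the safety run-in only permits further enrolment, and that promising for activity rests on the 6/20 rule.

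**Cost.** These are text changes, submitted as an amendment under Section 13.1, with no new patients or procedures. The downside of (a) is that a few patients may be unassessable and, under the all-treated denominator, count as non-responders.

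**Optional.** The sponsor could instead require a decrease beyond a pre-specified measurement-error margin. That redefines the primary endpoint, lowers sensitivity to small shrinkage, and fails if error is underestimated. In the model of step 3 with no growth, a margin that 15% of unchanged tumours would exceed at CV 10% (a 13.6% decrease) lets an unchanged-tumour arm pass 59% of the time if the CV is really 20%.

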1.2 Primary Objectives

- To determine the 1) safety, tolerability; and 2) response rate to window treatment with single agent nivolumab or nivolumab combined with ipilimumab using bidirectional measurements (product of longest 2 diameters of lesions) of primary and nodal lesions to be removed at the time of surgery

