7. BIOMARKER, CORRELATIVE, AND SPECIAL STUDIES

Biopsy confirmed squamous cell carcinoma is a requirement to be enrolled on this study. Tissue will be obtained prior to any treatment for research purposes whenever possible. If diagnostic biopsy was performed prior to enrollment on study (archival sample) and extra specimen is available from this biopsy, then this tissue may be obtained for use. A separate research biopsy is also strongly recommended – this can be a core biopsy of a lymph node or an in office biopsy. At the time of definitive surgical resection, after adequate tumor for pathological assessment has been harvested as deemed by the surgeon, remaining tissue will also be obtained for research purposes. If relevant, tissue may also be obtained at the time of first recurrence after surgery for study.

Biopsies/surgery should not generally be performed on Friday afternoons, as there may not be time for processing of tissue. However, specimens in formalin may be stored over the weekend and transported on Monday. Specimens in formalin should be stored at room temperature until shipment. Other investigative sites should follow institutional procedures for collecting and processing biopsy specimens.

When archival tissue is used for the pretreatment tissue specimen, formalin-fixed paraffin embedded block(s) and or unstained/unbaked slides (15-20 recommended, although fewer are acceptable), stored at room temperature and tissue scrolls should be obtained to facilitate correlative analyses.

In the case of fresh biopsies / surgical specimens, ideally at least 2-4 core biopsies / pieces of tumor tissue will be obtained:

- Half of the cores / specimens should be placed in 10% neutral buffered formalin tube.
- Half of the cores / specimens should be processed fresh for molecular analyses in media, snap frozen or frozen in RNAlater.

After being obtained, processing of the specimens is as follows:

- All samples should be de-identified and labeled with the Participant initials, Participant Study ID number, anatomical location from which tissue was obtained (e.g. lymph node, primary oral cavity tumor) and date of procedure.
- Specimens in formalin should be should be transferred to a pathology laboratory, placed in fixative at a 10:1 ratio and fixed for at least 24-48 hours. Thicker tissue samples may require longer fixation to create a formalin-fixed, paraffin embedded block.

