9. STUDY CALENDAR

Baseline evaluations are to be conducted within 3 weeks prior to start of protocol therapy (except for pregnancy test and baseline tumor biopsy, as detailed). If these screening assessments occur within 3 days before start of study treatment, then they may serve as the baseline cycle 1 day 1 values. Each treatment cycle will be 14 days long. Subjects may be dosed no less than 12 days between doses.

As detailed in the Study Calendar, a negative pregnancy test in women of child-bearing potential must be documented within 24 hours before the first dose of study medication.

Correlative tissue collection obtained before starting protocol therapy, should be performed if archival tissue is not available.

In the event that the participant's condition is deteriorating, laboratory evaluations should be repeated within 48 hours prior to initiation of the next cycle of therapy.

Assessments must be performed prior to administration of any study agent. Study assessments and agents should be administered within ± 3 days of the protocol-specified date, unless otherwise noted.

Scans must be done ≤ 4 weeks prior to the registration.

CONFIDENTIAL

This document is confidential. Do not disclose or use except as authorized.

	Screening	Week 1	Week 3	Presurgery/surgery (week 3-4)	Week 10-20	3 months after all treatment	3 months to 1 year ^l	1 year visit ^l	Survival follow up by phone ^m
Informed consent	X								
Medical History	X								
Physical exam (Ht, Wt, VS, PS) ^a	X	X	X			X ⁱ	X ⁱ	X ⁱ	
B-HCG ^b	X								
Routine labs ^d	X	X ^c	X	X					Xi
Screening labs/ECG ^e	X								
Adverse event evaluation ^f	X	X	X			X ⁱ	X ⁱ		
Radiologic evaluation ^g	X			X					
Correlative blood collection ^h	X			X	X		X		X
Correlative tissue collection	X ^j			X ^k					
Study Agent - Nivolumab		X	X						
Study Agent - Ipilimumab(cohort 2 only)		X							

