10.1.3 Methods for Evaluation of Measurable Disease

All measurements should be taken and recorded in metric notation, using a ruler, calipers, or digital measurement tool. All baseline evaluations should be performed as closely as possible to the beginning of treatment and never more than 4 weeks before the beginning of the treatment.

The same method of assessment and the same technique should be used to characterize each identified and reported lesion at baseline and during follow-up. Imaging-based evaluation is preferred to evaluation by clinical examination when both methods have been used to assess the anti-tumor effect of a treatment.

Clinical lesions. Clinical lesions will only be considered measurable when they are superficial or mucosal (e.g., skin nodules, oral cavity primaries and palpable lymph nodes). In these cases, documentation by color photography, including a ruler to estimate the size of the lesion, is recommended.

Conventional CT and MRI. These techniques should be performed with cuts of 10 mm or less in slice thickness contiguously.

10.1.4 FDG PET and PET/CT. The acquisition of FDG PET and FDG PET/CT scans should follow the NCI Guidelines for using FDG PET as an indicator of therapeutic response (L.K. Shankar, J.M. Hoffman, S. Bacharach, M.M., et al. Consensus recommendations for the use of 18F-FDG PET as an indicator of therapeutic response in patients in National Cancer Institute Trials. J Nucl Med, 47(6):901-903, 2006 or <http://www.ncbi.nlm.nih.gov/pubmed/16741317>). Patients should avoid strenuous exercise and be on a low carbohydrate diet for 24 hours prior to the scan. Patients should fast for 4 hours or longer prior to the FDG injection and should have a serum glucose

of less than 200 mg/dL at the time of FDG injection. A 10-20 mCi dose of FDG should be injected for typical adult patients.

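### A measured lesion biopsied after the baseline measurement can add a small, one-directional amount of false response, because any decrease counts and nothing orders the biopsy before the measurement

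*Combined protocol and SAP*

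**What the plan says.** **Response rule.** The primary objective (Section 1.2) uses "bidirectional measurements (product of longest 2 diameters of lesions) of primary and nodal lesions". Section 10.1.5.1 describes "measuring measurable and non measurable primary and nodal disease in at least two dimensions as determined by scan, clinical exam or pathology", then states "Responders will have demonstrated any decrease in overall tumor volume". Small, non-measurable lesions therefore count and no minimum decrease is set. Section 10.1.10 rules out central review.

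**Biopsy.** Section 7 says "A separate research biopsy is also strongly recommended – this can be a core biopsy of a lymph node or an in office biopsy", and for fresh tissue "ideally at least 2-4 core biopsies / pieces of tumor tissue will be obtained". No piece size is given. Archival tissue is acceptable (Section 5.2.3), and Section 9 calls for fresh tissue in one situation: "Correlative tissue collection obtained before starting protocol therapy, should be performed if archival tissue is not available".

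**Timing.** Section 9 allows scans up to 4 weeks before registration and exempts the baseline biopsy from the 3-week baseline window. Section 10.1.3 says "All baseline evaluations should be performed as closely as possible to the beginning of treatment", with a 4-week limit before treatment, and does not mention biopsy. Section 5.2.1 puts consent before any screening procedure.

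**Decision.** Section 14 calls an arm promising at 6 or more responders of 20, based on a one-sided 90% exact lower bound of at least 15%.

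**The concern.** The sequence of scan, research biopsy and first dose complies with the protocol. It is also a natural one, because a research biopsy has to follow consent while the scan may come from the routine work-up. In that sequence the patient can start treatment with slightly less tumour than the baseline records. With any decrease counted as response, the missing tissue can be credited to the drug. Random measurement error can move a patient either way, but removal of tissue moves the measurement only toward response. No section leaves a biopsied lesion out of the sum, adjusts for tissue taken, or sets a threshold that would absorb the loss. There is no untreated arm to show how often a decrease occurs without drug. At stake is the responder count that feeds the 6-of-20 decision in each arm.

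**Working it through.** **1. The plan's own figure.** The exact one-sided 90% lower bound for x of n is the 10th percentile of Beta(x, n − x + 1). For n = 20 it is 12.7% at x = 5 and 16.6% at x = 6, so 6 is the smallest count with a bound of at least 15%. The rule reproduces. P(X ≥ 6 | n = 20, p = 0.15) = 6.7%; at p = 0.30 it is 58% and at p = 0.40 it is 87%.

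**2. Ordering.** Sections 5.2.1, 5.2.3, 7, 9 and 10.1.3, read together, place both the biopsy and the baseline measurement before treatment. None places one before the other.

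**3. How much a biopsy can change the measurement.** All biopsy sizes here are assumptions.
- *Volume share*, n × (π/4) × width² × length ÷ (π/6 × D³), for a spherical lesion of diameter D. Two to four needle cores of 1.2 × 15 mm remove 0.8–1.6% at D = 20 mm. In a 10 mm node, with a 10 mm core path, they remove 4–9%. Two to four in-office pieces of 4 × 5 mm remove 3.0–6.0% at 20 mm, 1.5–3.1% at 25 mm and 0.9–1.8% at 30 mm.
- *Diameter product*, which is the endpoint. Tissue taken from inside a lesion, or from a face that defines neither diameter, changes the product by nothing. A loss of 1 mm from one diameter of a 20 mm lesion gives 19 × 20 ÷ 400 = 0.95, a 5% decrease. In a 10 mm node it gives 9 × 10 ÷ 100 = 0.90, a 10% decrease in that lesion. If products are summed (an assumption), a 20 mm primary plus that node goes from 400 + 100 = 500 to 490, a 2% decrease, which the rule still counts.

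**4. Effect on the decision.** Let s be the share of patients with a measured lesion biopsied after baseline, and q the chance that biopsy alone turns a non-responder into a scored responder. Then f = s × q, and the observed rate is p + (1 − p) × f. The documents give neither s nor q. At a true p = 0.15:

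| s | q | f | Observed rate | P(≥ 6 of 20) |
|---|---|---|---|---|
| 0 | – | 0 | 15.0% | 6.7% |
| 0.25 | 0.10 | 0.025 | 17.1% | 11% |
| 0.50 | 0.10 | 0.05 | 19.3% | 17% |
| 0.50 | 0.20 | 0.10 | 23.5% | 32% |

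**5. Biopsy against the wider problem.** Assume no drug effect, untreated growth g, SD 15% for measured change, and a biopsy shift b in the measurement. P(decrease) = Φ((b − g)/0.15).
- No biopsy loss: g = 10% gives 0.252 and P(≥ 6 of 20) = 0.39; g = 5% gives 0.369 and 0.81.
- g = 10%, b = 1%, half of patients affected: P(decrease) averages 0.263, and P(≥ 6 of 20) = 0.44.
- Upper-end illustration: g = 10%, b = 2–5%, every patient affected: P(decrease) = 0.297–0.369, and P(≥ 6 of 20) = 0.57–0.81.

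Under these assumptions the absence of an error margin does most of the damage, and biopsy adds to it.

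**The case against.** The strongest reply is that the endpoint is a product of two diameters, not tissue volume, and thin cores from a sizeable primary may leave both diameters unchanged. That stands. It means the volume shares in step 3 cannot be entered one-for-one as a shift, and the 0.57–0.81 range is an upper-end illustration only: it makes that substitution and has every patient biopsied after baseline. Archival tissue is accepted, so the true share is probably well below all. Section 10.1.3 asks for baseline evaluation close to treatment, which narrows the gap without ordering the two procedures. Swelling after biopsy could also offset some of the loss.

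Three stronger readings are tempting but unsupported.
- A reader might infer that a whole node could be excised between baseline and dose. Section 7 describes a node core or an in-office biopsy, not excision.
- A reader might count the diagnostic biopsy every patient has had. If it came before the baseline measurement, the tissue was already gone and there is no bias.
- A reader might infer that the marker–response correlations are distorted. That would need the tissue removed to be related to the marker, and nothing in the documents suggests it.

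A blanket rule that baseline must follow biopsy would also have a cost. Patients already scanned would need a second scan, and a baseline inflated by swelling that later settles would itself count as a decrease.

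**Conclusion.** The point holds as a limited one. The documents permit a measured lesion to be biopsied between the baseline measurement and the first dose, and the rule then allows tissue loss to contribute to a response. The direction is clear; the size is not known. It rests on two quantities the documents do not give: the share of patients with a fresh biopsy after baseline, and whether the tissue removed changes a longest diameter. The effect is likely to be little for thin cores in a large primary, and more for in-office pieces or small nodes. Plausible inputs range from no effect to a material rise in the chance of a false positive call (6.7% to 17% at f = 5%). The documents do not support saying that the 6-of-20 result will be driven by biopsies. They support saying that the plan, as written, could not show whether it was.

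**What to change.** 1. **Section 10.1.3, clinically measured lesions.** Take the baseline bidirectional measurement and photograph after the last pre-treatment biopsy, at the pre-dose week 1 exam already in the calendar, and note visible post-biopsy swelling. Section 5.2.2 lets screening within 3 days stand in for that visit, so the text should say that a biopsy in between calls for a new measurement.
2. **Lesions measured by imaging.** Where feasible, take the research biopsy before the baseline scan. Do not require a repeat scan.
3. **Section 14.** Section 7 already has biopsy date and anatomical site recorded with each specimen. Prespecify the primary response rate and the promising decision with and without patients who had a measured lesion biopsied between the baseline measurement and dose 1. In the reduced set, apply the same 15% lower-bound criterion instead of a fixed 6. For example, 15 patients need 5 responders: at p = 0.15, P(X ≥ 5 of 15) = 0.06, while P(X ≥ 4 of 15) = 0.18 exceeds 0.10.

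The primary analysis, n = 20 and the 6-of-20 threshold are unchanged. The cost is some scheduling constraint, possible swelling at a post-biopsy baseline, and lower precision in the sensitivity analysis. These steps do not cure the missing error margin, which needs its own answer.
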